6.2.4 Disease History

Frequency tabulations will be presented for disease history including tumor subtype and prior anti-cancer therapies.

6.2.5 Previous and Concomitant Medications

Previous medications include medications taken within 28 days prior to cycle 1 day 1 and all anticancer treatment received 28 days prior to IP administration. Previous medications are coded with WHO-DD, and will be summarized in descending percentage order by Preferred WHO Name (Ingredients), as well as by therapeutic subgroup (ATC 2nd level) and chemical subgroup (ATC 4th level) and preferred WHO name by dose level, phase, tumor type, and overall for the SAF.

Concomitant medications include medications taken after the first dose of study drug up until the 90 days follow-up visit. As with previous medication, concomitant medication will be summarized by dose level, phase, tumor type, and overall, in descending percentage order by Preferred WHO Name (Ingredients), as well as by therapeutic subgroup (ATC 2nd level) and chemical subgroup (ATC 4th level) and preferred WHO name for the SAF. Participants taking the same medication multiple times will be counted once per medication and investigational period. A medication which can be classified into several chemical and/or therapeutic subgroups is presented in all chemical and therapeutic subgroups.

6.2.6 Prior Radiation Therapy

Frequency tabulations of participants with prior radiation therapy will be presented for SAF.

6.2.7 Non-Medication Therapy

Frequency tabulations of participants with non-medication therapy and reason for use will be presented by dose level, phase, tumor type, and overall for SAF. Number of non-medication therapy received per participant will be summarized using descriptive statistics.

6.2.8 Prior and New Anti-Cancer Therapy

Frequency tabulations of participants with prior or new anti-cancer therapy will be presented for SAF.

6.3 Study Drug

6.3.1 Exposure

The following information on drug exposure will be presented with descriptive statistics (n, mean, standard deviation, median, minimum, maximum) for the SAF:

- Duration of exposure (days)
- Cumulative actual dose (# of cells)
- Number of cycles initiated

- Planned dose intensity
- Actual dose intensity
- Relative dose intensity (RDI; %); in addition to descriptive statistics, frequency tabulations will be presented for RDI for the following categories:
 - <50%
 - 50% to <=80%
 - >80%
 - Unknown

Number and percentage of participants with dose adjustments, or interruptions and reasons for dose adjustments and interruptions will be presented for the SAF.

6.4 Analysis of Efficacy

Efficacy analysis will be conducted on the FAS and RAS (RAS for response-related analyses, FAS for overall survival and other time-to-event analyses). Tumor related analyses are summarized based on RECIST 1.1 and iRECIST. Efficacy analyses will be summarized by dose level, phase, and tumor type. Swimmer plots will be produced displaying participants' overall disease response experience, and waterfall plots to display maximum tumor shrinkage rate.

6.4.1 Analysis of Primary Efficacy Endpoint

6.4.1.1 Objective Response Rate per iRECIST (iORR)

iORR with confirmed response by investigator assessment will be calculated for each group and its 95% confidence interval will be constructed by Clopper-Pearson method. To assess sensitivity, iORR will also be estimated and its 95% confidence interval will be constructed by Clopper-Pearson method for the endpoints:

- iORR with confirmed response by investigator assessment
- iORR with unconfirmed response by investigator assessment

6.4.2 Analysis of Secondary Efficacy Endpoints

6.4.2.1 Objective Response Rate per RECIST v1.1(ORR)

ORR for each group will be calculated and its 95% confidence interval will be constructed by Clopper-Pearson method for the endpoints of:

- ORR with confirmed response by investigator assessment
- ORR with unconfirmed response by investigator assessment

6.4.2.2 Disease Control Rate per iRECIST (iDCR)

iDCR for each group will be calculated and its 95% confidence interval will be constructed by Clopper-Pearson method by investigator assessment for the endpoints of:

- iDCR with confirmed response by investigator assessment
- iDCR with unconfirmed response by investigator assessment

6.4.2.3 Disease Control Rate per RECIST v1.1 (DCR)

DCR for each group will be calculated and its 95% confidence interval will be constructed by Clopper-Pearson method by investigator assessment for the endpoints of:

- DCR with confirmed response by investigator assessment
- DCR with unconfirmed response by investigator assessment

6.4.2.4 Overall Survival (OS)

OS will be estimated and summarized for each dose level and treatment group using Kaplan-Meier methodology for investigator assessments of radiological scans. OS will be also listed.

6.4.2.5 Progression-Free Survival per iRECIST (iPFS)

iPFS will be estimated and summarized for each group using Kaplan-Meier methodology for investigator assessments of radiological scans. iPFS will be listed.

6.4.2.6 Progression-Free Survival per RECIST v1.1 (PFS)

PFS will be estimated and summarized for each group using Kaplan-Meier methodology for investigator assessments of radiological scans. PFS will be listed.

6.4.2.7 Duration of Response per iRECIST (iDOR)

iDOR will be listed.

6.4.2.8 Duration of Response per RECIST v1.1 (DOR)

DOR will be listed .

6.5 Analysis of Safety

Safety analyses will be conducted using the SAF. Safety analyses will be summarized by dose level, phase, tumor type, and overall.

6.5.1 Dose Limiting Toxicities

Dose evaluation and dose escalation stopping rules based on the BOPIN design with target DLT rate of 0.30 and optimal interval of (0.236, 0.359) are as follows:

Action	Number of Participants Treated at Current Dose Level					
	3	4	5	6	7	8
Escalate dose if number of participants with DLT \leq	0	0	1	1	1	1
Stay at current dose level if number of participants with DLT =	1	1	-	2	2	2
De-escalate if number of participants with DLT =	2	2	2 or 3	3	3 or 4	3 or 4
Stop if number of participants with DLT \geq	3	3	4	4	5	5

DLT: dose limiting toxicity

6.5.2 Adverse Events

For the purpose of safety assessments in this study, events recorded during the pre-investigational period will be classified as Baseline Signs and Symptoms. All adverse events (AE) recorded on treatment including within 30 days from the last study treatment and serious adverse events (SAEs) on treatment including within 90 days of the last study treatment will be summarized.

Summaries and listings of SAEs and Serious TEAEs include SAEs upgraded by the sponsor based on review of the Sponsor's list of Always Serious terms if any upgrade was done.

The coding dictionary for this study will be MedDRA v26.0. It will be used to summarize AEs by SOC and PT. AEs will be graded using National Cancer Institute's Common Terminology Criteria for AEs (NCI-CTCAE).

An overview table will include the following details by dose level, phase, tumor type, and overall:

- Number and percentage of participants with TEAEs
- Number and percentage of participants with IP related TEAEs
- Number and percentage of participants with TEAE leading to death
- Number and percentage of participants with IP-related TEAE leading to death
- Number and percentage of participants with serious TEAEs and Astellas upgraded serious TEAE
- Number and percentage of participants with serious IP related TEAEs and Astellas upgraded serious IP related TEAE
- Number and percentage of participants with TEAEs leading to permanent discontinuation of study IP
- Number and percentage of participants with IP related TEAEs leading to permanent discontinuation of study IP
- Number and percentage of participants with CTCAE grade 3 or higher TEAE
- Number and percentage of participants with CTCAE grade 3 or higher IP related TEAE

The number and percentage of participants with TEAEs, as classified by SOC and PT will be summarized by dose level, phase, tumor type, and overall. Summaries will be provided for:

- DLTs within the DLT observation period
- TEAEs
- Deaths
- IP related TEAEs
- Serious TEAEs and Astellas upgraded serious TEAE
- IP related serious TEAEs and IP related Astellas upgraded serious TEAE
- TEAEs leading to permanent discontinuation of study IP
- IP related TEAEs leading to permanent discontinuation of study IP
- CTCAE Grade 3 or higher TEAEs
- IP-related CTCAE Grade 3 or higher TEAEs
- TEAEs excluding serious adverse events that equal to or exceed a threshold of 5% in any dose level
- common TEAEs that equal to or exceed a threshold of 5% in any dose level
- Late SAEs occurring beyond 30 days from last study treatment

The number and percentage of participants with TEAEs, and TEAEs leading to death, as classified by PT only, will be summarized by dose level, phase, tumor type, and overall.

AE summary tables will include participant counts as opposed to AE counts. If a participant experiences more than one episode of a particular AE, that participant will be counted only once for that event. If a participant has more than one AE that code to the same preferred term, the participant will be counted only once for that preferred term. Similarly, if a participant has more than one AE within a body system, the participant will be counted only once in that body system.

The number and percentage of participants with TEAEs, as classified by SOC and PT will also be summarized by NCI-CTCAE severity grade, and by relationship to study drug. In the participant count, if a participant has multiple TEAEs with the same SOC or PT, but with differing severity grade or relationship, then the participant will be counted only once with the worst severity grade and highest degree of relationship, however, if any of the severity grade or relationship values are missing then the participant will be counted only once with missing severity grade or relationship.

The number and percentage of participants with TEAEs, as classified by SOC and PT will be summarized by dose level for SAF.

All AEs, deaths, SAEs, withdrawals due to adverse events, and AEs for re-screened participants will be displayed in listings.

The list of adverse events to be summarized may change during the course of the study due to ongoing pharmacovigilance.

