5.2.1.5 Adverse Events (AEs)

AEs will be coded using MedDRA v26.0 and graded using NCI CTCAE.

A treatment-emergent adverse event (TEAE) is defined as an AE observed after starting administration of the IP and 30 days after the final administration of IP. An IP-related TEAE is defined as any TEAE with at least possible relationship (possibly or probably related) to study treatment as assessed by the investigator or with missing assessment of the causal relationship.

The number and percentage of participants with TEAEs, IP-related TEAEs, serious TEAEs, IP-related serious TEASs, TEAEs leading to withdrawal of treatment and IP related TEAEs leading to withdrawal of treatment will be summarized by SOC, preferred term and treatment group. The number and percentage of TEAEs by severity will also be summarized. The worst severity will be summarized if the same AE is recorded more than once for a participant. If an AE is observed with different relationships to study drug then the AE will be counted under its maximum relationship only. In case the AE relationship is not reported, it will be treated as the maximum relationship.

If the adverse event occurs on Day 1 and the onset check box is marked “Onset after first dose of study IP” or the onset check box is left blank, then the adverse event will be considered treatment emergent. If the adverse event occurs on Day 1 and the onset check box is marked “Onset before first dose of study IP”, then the adverse event will not be considered treatment emergent. If a participant experiences an event both during the preinvestigational period and during the investigational period, the event will be considered as TEAE only if it has worsened in severity (i.e. it is reported with a new start date). All adverse events collected that begin within 30 days after taking the last dose of study IP will also be counted as TEAE.

Immune-related AE (irAE) and infusion related reactions (IRR) will be considered as Adverse Events of Special Interest (AEsi). The list of events classified as AEsi may change during the study due to ongoing pharmacovigilance.

Time to first onset of irAE will follow the following algorithm:

Situation	Date of Event or Censor	Outcome
AE of interest observed	Date of first onset	Event
No AE of interest observed and treatment ongoing	Date of data cutoff	Censor
No AE of interest observed and treatment discontinued	Date of last dose + 30 days	Censor

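### SAP 6.5.2: in the TEAE tables by grade and by relationship, one missing value displaces a known Grade 3–5 or related record, and the relationship rule is not ordered against SAP 5.2.1.5

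*SAP*

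**What the plan says.** SAP 6.5.2 (Adverse Events) provides SOC/PT tables of TEAEs split by CTCAE grade and by relationship to study drug. A participant with several TEAEs in the same SOC or PT that differ in grade or relationship is handled as follows: "then the participant will be counted only once with the worst severity grade and highest degree of relationship". The same sentence then adds an exception: "if any of the severity grade or relationship values are missing then the participant will be counted only once with missing severity grade" or relationship.

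Two other sections bear on this.

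- **Severity.** SAP 5.2.1.5 says: "The worst severity will be summarized if the same AE is recorded more than once for a participant". Protocol 9.4.3.1 gives the same rule. Neither has an exception for a missing grade.
- **Relationship.** SAP 5.2.1.5 includes in the definition of an IP-related TEAE any event "or with missing assessment of the causal relationship". It says of an AE with differing relationships, "then the AE will be counted under its maximum relationship only", and then: "In case the AE relationship is not reported, it will be treated as the maximum relationship".

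SAP 6.5.2 also lists outputs that carry no such exception, among them an overview row, "Number and percentage of participants with CTCAE grade 3 or higher TEAE", and a SOC/PT summary of "IP-related CTCAE Grade 3 or higher TEAEs".

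**The concern.** **Grade.** The exception discards information that the missing value cannot alter. If the known grade is 5, nothing the missing grade could be would change the worst grade. If it is 3 or 4, the participant has Grade 3 or higher whatever the missing grade is. Reporting these participants as missing departs from the worst-severity principle in the first half of the same sentence.

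**SOC against PT.** The exception applies within a SOC as well as within a PT. An ungraded event under one PT can therefore remove a participant from the SOC's Grade 3–5 rows while leaving that participant in the Grade 3–5 rows of another PT in the SOC.

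**Relationship.** If SAP 5.2.1.5 is applied first, nothing is left missing and the relationship part of the 6.5.2 exception is redundant. If 6.5.2 is applied to the raw values, it contradicts 5.2.1.5. The SAP states no order, so two programmers could each follow it and produce different tables.

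Safety and tolerability are a primary objective (Protocol Section 3, SAP 2.1). At stake are tables that can understate severe events (and, on the literal reading, related events) and that can disagree with other tables in the same report.

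**Working it through.** The plan gives no figure to reproduce. The check applies the stated rules to small record sets.

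**1. Grade pairs.** Inputs: the SAP 6.5.2 exception, and the worst-grade rule applied to non-missing values.

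| Records in the same SOC or PT | SAP 6.5.2 as written | Worst non-missing grade |
|---|---|---|
| 1, missing | missing | 1 |
| 2, missing | missing | 2 |
| 3, missing | missing | 3 |
| 4, missing | missing | 4 |
| 5, missing | missing | 5 |

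All 5 pairs are shown as missing, and 3 of the 5 hide a known Grade 3 or higher.

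**2. Relationship.** Inputs: the SAP 6.5.2 exception and the SAP 5.2.1.5 missing-relationship rule.

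| Records | 6.5.2 on raw values | 5.2.1.5 first, then 6.5.2 |
|---|---|---|
| yes, missing | missing | related |
| no, missing | missing | related |
| missing, missing | missing | related |

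The two orders disagree in 3 of 3 cases.

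**3. SOC against PT.** Participant A has PT1 at Grade 4 and PT2 ungraded, both in one SOC. Participant B has PT1 at Grade 3.

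- PT1 row under 6.5.2: A and B both count, so 2 with Grade 3 or higher.
- SOC row under 6.5.2: A is moved to missing, so 1 with Grade 3 or higher.
- With the worst non-missing grade: 2 and 2.

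The separate Grade 3 or higher SOC/PT summary has no exception and shows 2 for the SOC. As percentages of treated participants:

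- n = 6 (minimum at the MTD/RP2D dose level, Protocol 4.1.5.2): 2/6 = 33.3% against 1/6 = 16.7%.
- n = 12 (planned per arm in phase 1, Protocol 9.2): 2/12 = 16.7% against 1/12 = 8.3%.

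**4. Frequency, as illustration only.** The documents give no missing rate. Assume that each record is missing its grade independently with probability m, and that a participant with one known Grade 3 or higher record has j other records in the SOC. The chance of displacement is 1 − (1 − m)^j.

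| m | j = 1 | j = 4 |
|---|---|---|
| 1% | 1.0% | 1 − 0.99^4 = 3.9% |
| 2% | 2.0% | 1 − 0.98^4 = 7.8% |
| 5% | 5.0% | 1 − 0.95^4 = 18.5% |

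The values of m and j and the independence are all assumptions.

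**The case against.** **The important outputs are safe.** Grade 3 or higher and IP-related events have their own rows and tables, deaths are summarised separately, and all AEs are listed. This stands, and it limits the point to the by-grade and by-relationship tables. It does not remove the possibility that those tables contradict the others.

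**Missing values should be rare.** Protocol 10.3.3 obliges the investigator to assess causality for every event and points to a default of no for an SAE with too little information. Protocol 10.3.4 requires grading, 10.3.6 makes causality part of the minimum SAE report, and 10.1.7 provides for data checks. Protocol 7.3.1 has an event relisted when its grade changes, so those repeat records exist because a grade was assigned. All of this stands as to frequency, although relisting also means that participants with several records are to be expected. A missing-data rule matters only when data are missing, and this one then hides known severe events.

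**Derive first, then tabulate.** SAP Section 5 defines endpoints and Section 6 tabulates them, so the natural reading applies 5.2.1.5 first and leaves only redundant wording on relationship. That is reasonable, but the SAP does not say so.

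**The SOC level is not covered by the worst-severity rule.** SAP 5.2.1.5 and Protocol 9.4.3.1 concern repeats of the same AE, not different PTs pooled in a SOC. This is correct: at SOC level the worst-grade rule is the 6.5.2 sentence itself, and no explicit missing-grade rule is contradicted. The SOC/PT incoherence follows regardless.

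**The denominator is a choice.** SAP 6.1 and Protocol 9.4.1 base category percentages on participants with no missing data. If that applied here, the displaced participant would leave the denominator, giving 1/5 = 20.0% or 1/11 = 9.1%. A convention under which categories add up to 100% does not fit AE incidence tables, and the count mismatch of 2 against 1 holds under any denominator.

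**For a known Grade 1 or 2, missing is defensible,** because the ungraded event could be worse. This stands and is why the fix needs a footnote.

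**Conclusion.** The concern holds. Followed exactly, SAP 6.5.2 turns a known Grade 3, 4 or 5 into missing whenever one record in the same SOC or PT is ungraded, and it can make a SOC show fewer severe cases than one of its own PTs. For relationship, the literal clause conflicts with SAP 5.2.1.5; if 5.2.1.5 is applied first, the clause is merely redundant. The order should be stated.

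These conclusions follow from the rules alone and need no assumed missing rate. How many participants would be affected cannot be derived from the documents and may be few or none; the percentages in step 4 are illustrative only. The correction should be made, but the point does not affect the MTD, the overview table, the Grade 3 or higher and IP-related summaries, the death summaries or the listings.

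**What to change.** Replace the exception in SAP 6.5.2 with a rule to this effect: the participant is counted once at the worst non-missing grade; missing grade is shown only if all grades for that SOC or PT are missing; a footnote gives the number of participants with any missing grade; a missing relationship is counted as the maximum relationship (related), as in Section 5.2.1.5.

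Taking the worst non-missing grade imputes nothing, so it fits the general no-imputation principle in Protocol 9.6. The relationship rule is already in the SAP.

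The downside is that an ungraded event beside a graded one appears only in the footnote and the listings. This matters for a known Grade 1 or 2 (2 of the 5 pairs), where the reported grade may be too low, so the footnote should not be dropped.

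The cost is one SAP sentence, one table footnote and the programming of the by-grade and by-relationship tables, with no new data. SAP Section 1 has the final SAP approved before database hardlock and changes to the planned analyses documented in the CSR, so there is a route for the change in either case.

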6.5.3 Adverse Events of Special Interest (AEsi)

The number and percentage of participants with Adverse Events of Special Interest (AEsi) such as IRR, irAE, and as classified by SOC and PT, will be summarized by dose level, phase, tumor type, and overall.

6.5.4 Clinical Laboratory Evaluation

The baseline visit is the last measurement taken prior to initial study IP administration.

Frequency tabulations of qualitative clinical laboratory variables will be presented at each visit.

Laboratory results will also be graded using NCI-CTCAE, where possible. Following the [Table 6](#) in [section 5.2.1.6](#), parameters that have criteria available for both low and high values, i.e., hypo- and hyper-, will be summarized for both criteria. The same participant can be counted for both values if the participant has different laboratory values meeting each criterion. NCI-CTCAE grade of laboratory evaluations will be summarized by number and percentage of participants for each visit. Shift tables of NCI-CTCAE grade change from baseline to worst post-baseline grade will also be presented. The number and percentage of participants with grade 3 or 4 laboratory test results will be summarized by dose level, phase, tumor type, and overall, and laboratory parameter (the name of the adverse event associated with the abnormal laboratory test result) will be presented.

Laboratory results will be listed.

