- l. Thyroid panel including triiodothyronine or free triiodothyronine, free thyroxine and thyroid stimulating hormone will be measured prior to receiving pembrolizumab only for participants in the combination cohort (C1D1, C2D15, C4D1 and C5D15). If the thyroid panel is to be measured on same day of pembrolizumab dosing (ex. C4D1, pembrolizumab monotherapy dosing visit), the thyroid panel must be measured prior to receiving pembrolizumab. Thyroid panels assessed on C1D1 and C2D15 only apply for the combination therapy cohort.
- m. Enrollment or randomization will be done via IRT system after confirmation of eligibility and prior to dosing.
- n. Whole blood for optional PGx study may be collected at C1D1 prior to IP administration.
- o. See [Table 6](#) for collection schedule for ASP7517 monotherapy and ASP7517 and pembrolizumab combination therapy.
- p. Archival tumor specimen at a minimum of 1 FFPE tumor tissue block with adequate viable tumor cells (preferred) OR a minimum of 20 FFPE unstained serial slides are required.
- q. Same technique (CT/MRI) used at screening should be utilized throughout the study. Imaging should include chest, abdomen and pelvis, as well as any other anatomical region appropriate for the participant's disease. Scans performed prior to informed consent as standard of care are acceptable as screening scans, if done within 28 days prior to C1D1.
- r. In both the monotherapy and combination cohorts, each participant must remain at the site facility for 4 h following the participant's first dose of ASP7517. For the next dose (2nd dose) or additional subsequent monotherapy with ASP7517, participants must remain at the site facility for at least 2 h after ASP7517 dosing.
- s. In the combination therapy arm, pembrolizumab will be administered as an intravenous infusion over 30 min followed by ASP7517 administration at least 1 h after pembrolizumab administration.
- t. If the participant will discontinue treatment due to meeting protocol criteria of CR after completion of Cycle 4 or a participant completes all 6 cycles of ASP7517, then all visits in the treatment cycle should be completed and the EOT visit will be performed 7 days (+ up to a 7-day window) after the last planned visit.
 - If participant has CR after completing Cycle 4, the EOT visit would be performed between C4D22 and C4D29.

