2.3.1.4 Kidney

Increased serum creatinine was seen 1 day after the first dose. This finding was completely resolved 7 days after the first dose. In addition, histological assessment showed basophilic tubules and infiltration of mononuclear cells 7 days after the second dose. These histological findings were completely resolved 28 days after the second dose. The presence of basophilic tubules is interpreted as regeneration of renal tubules. The standard monitoring of kidney function parameters (creatinine, blood urea nitrogen) is recommended in clinical studies.

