2.3.1.6 Infusion-related Reactions

In nonclinical studies with ASP7517, IRRs/cytokine-release syndrome (CRS) was not seen. However, there are potential toxicities with intravenous infusion immunotherapy and the exact mechanism causing standard infusion reactions is unclear, but most reactions appear to arise from cytokine release from immune-mediated mechanisms [Lee et al, 2014].

The symptoms and signs associated with a standard infusion reaction include fever, shaking chills, flushing and/or itching, changes in heart rate and blood pressure, shortness of breath or chest discomfort, pain in back or abdomen, nausea, vomiting and/or diarrhea and skin rash.

In addition to the signs and symptoms associated with a standard infusion reaction, CRS may result in neurologic signs and symptoms such as mental status changes, confusion and delirium. Renal and hepatic manifestations may include azotemia, elevated transaminases and hyperbilirubinemia, respectively. Coagulation parameters may also be affected and manifested by elevated D-dimer and hypofibrinogenemia, with or without bleeding. In addition, tumor lysis syndrome may also be associated with CRS [Lee et al, 2014]. Participants should be closely monitored for IRRs and CRS and appropriately managed per standard of care.

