9.4.3.2 Laboratory Assessments

For quantitative clinical laboratory measurements (hematology and biochemistry), descriptive statistics will be used to summarize results and change from baseline by monotherapy and combination therapy arms, and dose level, and overall and time point. Shifts from baseline to the worst grade based on NCI CTCAE 5.0 in laboratory tests will also be tabulated.

Laboratory data will be listed.

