5.2.1.6 Laboratory Assessments

Clinical laboratory variables for hematology, chemistry including liver function test, coagulation, urinalysis, and bone marrow will be collected during the conduct of the study as listed in [Table 6](#) below.

Additional laboratory tests should be performed according to institutional standard of care.

Table 6 Laboratory Assessments

Clinical Laboratory Tests

Panel/Assessments	Parameters to be Analyzed	NCI-CTCAE Grading (Hyper/Hypo)
CBC with Differential	Hematocrit (Hct) Hemoglobin (Hgb) Platelet count Red blood cell count (RBC) White blood cell count (WBC) White blood cell count differential Absolute neutrophil count Absolute lymphocyte count	NA Both Hypo NA Both NA Hypo Both
Biochemistry	Sodium (Na) Potassium (K) Chloride (Cl) Bicarbonate (HCO3) Blood urea nitrogen (BUN) Creatinine (Cr) Glucose (Gl) Calcium (Ca) Phosphorus Magnesium (Mg) Albumin (Alb) Total protein (T Prot) Alkaline phosphatase (ALP) Lactate dehydrogenase (LDH) Creatine phosphokinase (CPK) Liver function tests including*: Bilirubin total (TBL) Alanine aminotransferase (ALT) Aspartate aminotransferase (AST)	Both Both NA NA NA Hyper Both Both NA Both Hypo NA Hyper NA Hyper Hyper Hyper Hyper
Table continues next page		

Panel/Assessments	Parameters to be Analyzed	NCI-CTCAE Grading (Hyper/Hypo)
Urinalysis	Color Appearance Specific gravity pH Bilirubin Blood Glucose Ketones Leukocyte esterase Nitrite Protein Urobilinogen	NA NA NA NA NA NA NA NA NA NA NA NA
Urine/Serum Pregnancy Test *	hCG (Positive/Negative)	NA
Coagulation Profile (PT/INR, D-Dimer, Fibrinogen)	Activated partial thromboplastin time (aPTT) International normalized ratio (INR) Prothrombin time (sec) (PT) Fibrinogen D-Dimer	Hyper Hyper NA NA NA

eCRF: electronic case report form; hCG: human chorionic gonadotrophin.

* Local results will be collected and entered into the eCRF.

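### SAP 6.5.4 omits the descriptive and change-from-baseline laboratory tables that protocol 9.4.3.2 plans for hematology and biochemistry; coagulation and thyroid have smaller, separate gaps

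*SAP*

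**What the plan says.** Protocol 9.4.3.2 commits to this: "For quantitative clinical laboratory measurements (hematology and biochemistry), descriptive statistics will be used to summarize results and change from baseline". The summaries are to be broken down by therapy arm, dose level and time point, with an overall summary. The section adds shifts from baseline to worst CTCAE grade and a listing.

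SAP 6.5.4 gives four kinds of output:

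- Qualitative variables: "Frequency tabulations of qualitative clinical laboratory variables will be presented at each visit".
- Graded results: "Laboratory results will also be graded using NCI-CTCAE, where possible". This covers grade by visit, shift to worst grade, and counts of grade 3 or 4.
- A listing: "Laboratory results will be listed".
- Threshold tables for ALT, AST, bilirubin and ALP (SAP 6.5.4.1).

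SAP Table 6 (section 5.2.1.6) marks each test as graded high, graded low, both, or NA.

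Laboratory results are part of the primary safety endpoint in both documents (protocol Table 8, SAP 2.1). Chemistry, hematology and coagulation are named there; thyroid is not.

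**The concern.** The protocol plans a summary of measured values. The SAP has no such table for any quantitative laboratory test. A test marked NA in Table 6 therefore has no table at all, and a graded test shows only movements that cross a grade boundary.

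The protocol's own risk section gives reasons to look at values in this study:

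- **Kidney (2.3.1.4):** "The standard monitoring of kidney function parameters (creatinine, blood urea nitrogen) is recommended in clinical studies". BUN is marked NA.
- **LDH (2.3.1.8):** an LDH increase is among the events reported with related immunotherapies. LDH is marked NA.
- **Platelets (2.3.1.2):** counts fell in a dose-related way one day after dosing and were above baseline at day 7. Table 6 grades platelets for low values only.
- **Cytokine release (2.3.1.6):** "Coagulation parameters may also be affected and manifested by elevated D-dimer and hypofibrinogenemia, with or without bleeding". Fibrinogen and D-dimer are both marked NA.
- **Thyroid (1.3, Table 1, thyroid footnote):** "free thyroxine and thyroid stimulating hormone will be measured prior to receiving pembrolizumab" in the combination cohort. Table 6 has no thyroid row.

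A report that follows the SAP as written would leave a reader to find any pattern in these tests by going through listings.

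**Working it through.** The plan states no numerical figure on this point, so the check compares the two documents and counts entries.

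**Step 1. Outputs specified.**

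| Output | Protocol 9.4.3.2 | SAP 6.5.4 |
|---|---|---|
| Descriptive statistics of values | Yes, hematology and biochemistry | Not specified |
| Change from baseline in values | Yes, hematology and biochemistry | Not specified |
| Shift to worst CTCAE grade | Yes | Yes |
| Grade by visit; grade 3 or 4 counts | Not mentioned | Yes |
| Frequencies of qualitative tests | Not mentioned | Yes |
| Listing | Yes | Yes |

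**Step 2. Quantitative entries in SAP Table 6.**

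| Panel | Entries | NA | Graded |
|---|---|---|---|
| CBC | 8 | 3 (hematocrit, RBC, WBC differential) | 5 |
| Biochemistry | 18 | 6 (chloride, bicarbonate, BUN, phosphorus, total protein, LDH) | 12 |
| Hematology and biochemistry together | 8 + 18 = 26 | 3 + 6 = 9 | 5 + 12 = 17 |
| Coagulation | 5 | 3 (PT, fibrinogen, D-dimer) | 2 (aPTT, INR) |
| All | 26 + 5 = 31 | 9 + 3 = 12 | 17 + 2 = 19 |

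**Step 3. Apply the protocol's scope.** The commitment in 9.4.3.2 is limited to hematology and biochemistry. Protocol Table 14 lists coagulation and thyroid as separate panels.

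- Nine entries lose a planned summary and are only listed.
- Seventeen entries keep grade tables but lose the planned value and change summaries.
- Three coagulation tests (PT, fibrinogen, D-dimer) have no summary in either document. This is a shared gap, not a departure from the protocol.
- The thyroid panel was not promised a descriptive summary either. It is in protocol Table 14 and is scheduled before pembrolizumab on C1D1, C2D15, C4D1 and C5D15, but it is missing from SAP Table 6. Whether it would even be listed is unclear.

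MCV, MCH and MCHC are hematology tests in protocol Table 14 that also have no row in SAP Table 6.

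**Step 4. Does another SAP section supply the tables?** SAP 6.1 says which statistics to use for continuous variables. It commits to no laboratory table and does not mention change from baseline. Where the SAP wants both, it says so: 6.5.5 for vital signs and 6.5.6 for ECG. The neighboring laboratory section does not.

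**Step 5. Platelets as an example.** Protocol Table 1 schedules hematology on Days 2 and 8 of Cycle 1 in dose escalation, close to the preclinical fall and rise. The data to look for the pattern will exist. The grade tables can show the fall only where it crosses a grade boundary, and cannot show the rise at all. Change from baseline by visit and dose level would show both.

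**The case against.** The case for leaving the SAP alone has several parts.

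- **Graded counterparts exist.** Hemoglobin is graded beside hematocrit and RBC, neutrophils and lymphocytes beside the differential, creatinine beside BUN, and INR beside PT. This stands in part. These are related measures, not the same ones, but anemia, kidney and clotting safety do have tables. Of the nine, chloride, bicarbonate, phosphorus, total protein and LDH (9 - 4 = 5) have no such direct counterpart.
- **Clinical events are tabulated elsewhere.** SAP 5.2.1.5 and 6.5.3 make infusion-related reactions and immune-related AEs events of special interest, with tables by SOC and PT. Diagnosed infusion reactions and immune-related thyroid disorders would appear there. Liver tests have their own threshold analysis. This stands.
- **No decision rule depends on these tables.** No DLT, MTD or RP2D rule uses a mean laboratory change. This stands.
- **The study closed early.** SAP section 7 says that the number of analyses was reduced, and the separate TLF specifications cited in SAP 6.1 are not available here. This may explain the omission, but the SAP does not say that it does.

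A reader might infer three stronger points that the documents do not support. The first is that all twelve NA entries and the thyroid panel lost a promised summary; the protocol's wording covers only nine of them. The second is that the thyroid panel belongs to the primary endpoint; it is not named there. The third is that the sponsor removed the laboratory tables at early closure without recording it. The revision history describes version 2.0 against a version 1.0 that is not available, so its silence cannot show when or why the tables were left out. Both documents also leave departures to be explained in the CSR (protocol 9.4, SAP section 1).

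**Conclusion.** The protocol and SAP disagree on how part of a primary safety endpoint is summarized, and the point should be fixed. Its size is 9 of 26 hematology and biochemistry entries with no table where the protocol plans one, and 17 of 26 reduced to grade tables. BUN and LDH are the clearest losses among the ungraded tests. Among the graded ones it is the platelet count, where a rise cannot be seen. The coagulation gap (3 of 5 tests) and the missing thyroid row are secondary omissions.

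What is lost is summary, not data: hematology, biochemistry and coagulation results stay in the listings. The conclusion rests on reading SAP 6.1 as a convention and not as a commitment to laboratory tables, and on the TLF specifications not adding them. If they do add them, the SAP text still needs to say so.

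**What to change.** In SAP 6.5.4, restore the protocol's tables for quantitative hematology and biochemistry: n, mean, SD, median, minimum and maximum of values, and change from baseline, by visit, dose level and therapy.

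As a small addition and not a restoration, apply the same tables to the coagulation tests, and add the thyroid panel to Table 6 for the combination arm.

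Deleting bone marrow from the lead-in to Table 6 ("coagulation, urinalysis, and bone marrow will be collected during the conduct of the study") is clerical; the protocol's laboratory table and schedules contain no such test.

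The data are already collected and the tables are standard. The cost is a few more pages in a report that the sponsor has chosen to shorten. If the sponsor prefers the shorter report, the alternative is to state the reduction and its reason in SAP section 7 and in the CSR. That would resolve the contradiction but would leave BUN and LDH without a table and a platelet rise unseen in any table.
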